will be determined by the distribution of the data. In our previous study [9], 6% of patients referred to a H@H service had died within 2 days, 40% within one month, 62% within 2 months, and the remaining 38% were refer red over 2 months before death. Resource use will be converted to costs using national tariffs [32]. Informal care will be valued using replacement cost methods. For each of the model types of H@H service provision, an average cost/day of treatment will be estimated for the 4-6 time periods respectively. This will provide descriptive cost data, independent of expected survival time that can be compared between H@H model types. Alongside this analysis, a comparison of the average survival times for patients in each of the H@H models will be provided. However, caution will need to be taken when trying to infer a total cost of service from the survival data and average cost of service/day. Costs will be presented as means and median, given the typical skew in the distribution of costs. Comparison of costs between H@H model will be assessed for significance using Mann Whitney test. Sensitivity analysis for costs will be handled deterministically, varying the amount of resource use between their upper and lower limits for each H@H model type. Costs will be analysed in relation to outcomes from different models in a cost –consequences framework.

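### The only stated cost sensitivity analysis varies measured resource use between undefined limits and leaves the valuation choices fixed

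*Protocol*

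**What the plan says.** All of this is in Protocol section 8.4 (Economic analysis).

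- **Valuation.** "Resource use will be converted to costs using national tariffs", and "Informal care will be valued using replacement cost methods". Neither sentence gives an alternative value or a range.
- **Cost measure.** For each model type, "an average cost/day of treatment will be estimated for the 4-6 time periods respectively", with the periods defined by survival time.
- **Reporting and comparison.** "Costs will be presented as means and median, given the typical skew in the distribution of costs". The section also names the test between model types: "Comparison of costs between H@H model will be assessed for significance using Mann Whitney test".
- **Cost sensitivity.** "Sensitivity analysis for costs will be handled deterministically", by "varying the amount of resource use between their upper and lower limits for each H@H model type". The protocol states no other sensitivity analysis for costs.

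The protocol does not say whether the limits are the minimum and maximum, quartiles, confidence limits or externally chosen plausible values. Resource use itself is collected from carers with the customised AHCR, by recall for up to two months before recruitment and then by fortnightly telephone contact (sections 6.2 and 8.4).

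**The concern.** A deterministic sensitivity analysis suits inputs that the analyst has chosen. Here the amount of resource use is mostly data: each patient's use is recorded, and the uncertainty in a model's mean comes from sampling and from reporting error. The chosen inputs are the price put on an hour of unpaid care and the tariffs, and the stated analysis varies neither.

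Unpaid care matters in this design. Section 5.1.2 excludes patients without a suitable lay carer, and section 5.2 defines a carer as someone giving daily support at home. An informal-care component is therefore to be expected in essentially every patient's cost. If models substitute paid for unpaid care to different degrees, the cost comparison can depend on that price.

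The protocol intends to relate costs to outcomes in a cost-consequences framework (section 8.4), and section 11 expects guidelines that also address cost. A reader of those guidelines would want two things: how precisely the difference in mean cost is known, and whether it depends on how unpaid care is priced. As written, the analysis need not show the first and does not address the second.

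**Working it through.** **Sample size to use.** The protocol gives no figure for the cost analysis. Its only sample size is for the QODD (section 8.1): difference 10, SD 16.41, at least 44 per model type, 66 after 33% drop-out. With two-sided alpha 0.05 and power 0.80 (assumed, since neither is stated):

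n = 2 × (1.96 + 0.84)² × 16.41² / 10² ≈ 42.2, rounded up to 43.

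The exact t calculation gives 44 (power 0.807), and 44 / 0.67 = 65.7, rounded up to 66. The stated figures reproduce, so 44 per model is used below. A survival-period cell holds about 44 / 4 = 11 patients.

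**Assumptions.** The protocol gives no cost spread and no cost ratio. Cost per day is taken as lognormal, in line with the skew the protocol expects. The spread is given as a log-SD σ or as a coefficient of variation, CV = √(exp(σ²) − 1). So σ = 0.6, 0.8 and 1.0 give CV ≈ 0.66, 0.95 and 1.31.

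**Why data ranges rarely separate.** In 44 observations the largest lies roughly Φ⁻¹((44 − 0.375)/(44 + 0.25)) ≈ 2.2 SD above the centre on the log scale, and the smallest as far below. Two ranges separate only when ln(ratio) exceeds about 4.4σ. At σ = 0.6 that is 4.4 × 0.6 = 2.64, a ratio of about 14.

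**Simulated overlap of two models' intervals, n = 44 per model** (10,000 replicates):

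| CV | True ratio | Limits = min–max | Limits = quartiles | Limits = 95% CI of mean |
|---|---|---|---|---|
| 0.5 | 2 | 1.000 | 0.285 | 0.001 |
| 0.5 | 3 | 1.000 | 0.000 | 0.000 |
| 1.0 | 2 | 1.000 | 0.952 | 0.306 |
| 1.0 | 3 | 1.000 | 0.470 | 0.014 |
| 1.5 | 2 | 1.000 | 0.993 | 0.655 |
| 1.5 | 3 | 1.000 | 0.854 | 0.211 |

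In terms of σ from 0.6 to 1.0, still with 44 per model:

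- Min–max ranges overlap in 100% of studies up to a three-fold ratio.
- Quartile limits overlap in 4 to 77% at three-fold.
- Confidence limits of the two means overlap in 2 to 54% at two-fold.
- A 95% interval for the difference in means includes zero in 0.1 to 27% at two-fold.

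**Where ranges do separate.** Min–max overlap falls to 0.945 at five-fold and 0.224 at ten-fold with CV 0.5, and to 0.063 at five-fold with CV 0.3. At σ = 0.3 it is 87% at three-fold.

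**Effect of sample size.** A data range widens as patients are added. At CV 0.5 and a ten-fold ratio, min–max overlap is 0.026, 0.224 and 0.366 with 11, 44 and 66 per model. Confidence limits do the opposite. At CV 1.0 and two-fold, their overlap falls from 0.880 to 0.306 to 0.115. The high value at 11 is genuine imprecision in a small survival-period cell.

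**Valuation.** Write a model's mean cost per day as P + w·h, with P paid services, h informal-care hours and w the replacement price. The difference between models A and B is (P_A − P_B) + w(h_A − h_B). If A has dearer paid care and fewer unpaid hours, the sign changes at w* = (P_A − P_B)/(h_B − h_A). Moving h between each model's own limits at one fixed w does not show where w lies relative to w*.

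**The case against.** The strongest reply is that the overlap result depends on a reading the text does not impose. Section 8.4 does not call the limits observed, minimum or maximum, and it sets no rule that judges a cost ordering by overlap. The analysis could simply present a low and a high cost for each model. Between-model comparison is assigned to the Mann–Whitney test, whose simulated power at a two-fold difference is 0.96 (n = 44, CV 1.0). All of that stands. A reader might infer that the analysis makes models overlap whatever the truth, but neither the text nor the figures support this: models separate under confidence limits, often under quartiles, and even under min–max when spread is low.

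The second reply is that varying quantities is legitimate. Use is reported by carers, partly from two months' recall, and shared service costs rest on the finance manager's guidance. Informal care is itself a recorded quantity, so its cost moves when quantities move. This also stands in part. A common proportional change in hours across all models would even be equivalent to changing the price. The protocol, however, uses limits specific to each model type, which is a different exercise.

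The third reply is that the economic analysis is descriptive and that a later plan could define the limits and add valuation scenarios. That lowers the stakes. It does not change what the protocol fixes as the input to vary. Nor does the Mann–Whitney test fill the gap, because it gives no interval for a difference in mean cost and says nothing about the pricing of unpaid care.

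**Conclusion.** The point holds in a limited form. The protocol directs its one cost sensitivity analysis at measured quantities with undefined limits and leaves the valuation choices unvaried.

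The size depends on what the limits mean. As a data range, they describe patient-to-patient spread, and the ranges of two models overlap in every simulated study up to a three-fold difference. As confidence limits of the mean, most of that problem disappears, and what remains is a loss of sharpness compared with an interval for the difference. These figures rest on assumed lognormal costs, log-SD 0.6 to 1.0 and 44 patients per model.

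It would go too far to say that the valuation assumptions will go untested in this study. Only the protocol is available, and it is silent on the matter. Severity is low to moderate: the analysis is descriptive, and nothing ties the guidelines to this one sensitivity analysis.

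**What to change.** Replace the sensitivity sentence in section 8.4 with wording to this effect: sampling uncertainty in cost will be shown by bootstrap 95% confidence intervals for the difference in mean cost per day between model types. Deterministic sensitivity analysis will vary the valuation assumptions, with informal care at a low and a high replacement cost and excluded, and unit tariffs over a stated range. If resource quantities are still varied to reflect recall error, their limits will be defined in advance.

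The cost is wording and some extra runs on data already planned for collection: three informal-care scenarios plus a low and a high tariff scenario make five. Reporting grows somewhat. Four model types give 6 pairs, so 4 to 6 survival periods give 24 to 36 intervals, which fit in one supplementary table. Intervals in small survival-period cells will be wide and should be presented as such.

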8.5 Consensus Events

Guided by realist evaluation [11], two national consensus workshops, with up to 60 participants attending in each, will be used to validate interpretation of the data and to refine our understanding of the specific features of H@H models that work, for whom, and under what circumstances. In order to maximise attendance from stakeholders across the country, one workshop will be help in the south (e.g. London) and one will be held in the north (e.g. Leeds). Participants will be identified through the NAHH and our project steering group. It is anticipated that stakeholders will include service providers, commissioners, CCG End of Life Care leads, and service user representatives. Emerging findings and relationships between context, mechanisms and outcomes will be presented to stakeholders [17]. The explicit aim of the workshops will be to refine context -mechanism-outcome configurations and develop consensus on what type of H@H services are likely to work best, and in what circumstances. The workshops will also contribute to translating findings into information that is relevant to managers and commissioners of Hospice at Home services

9. ETHICS AND REGULATORY ISSUES

9.1 ETHICS APPROVAL

The Chief Investigator has obtained approval from the NREC London – Queens Square the Health Research Authority and NHS Research Ethics Committee (ref 17/LO/0880) to undertake this study. The study must be submitted for Site Specific Assessment (SSA) at each participating site. The study will be conducted in accordance with the recommendations for physicians involved in research on human subjects adopted by the 18th World Medical Assembly, Helsinki 1964 and later revisions. As patients may not be able to consent for themselves, the study will also comply with the Mental Health Act 1983.

9.2 CONSENT

Consent to enter the study will be sought from each participant or relevant consultee only after a full explanation has been given, an information leaflet offered and time allowed for consideration. The right of the participant to refuse to participate without giving reasons will be respected. All participants are free to withdraw at any time without giving reasons and without prejudicing their care.

9.3 CONFIDENTIALITY

The Chief Investigator will preserve the confidentiality of participants taking part in the study under the Data Protection Act.

9.4 SPONSOR AND INDEMNITY

The University of Kent will act as the Sponsor for this study. Delegated responsibilities will be assigned to the Hospice Sites taking part in this study.

The University of Kent holds negligent harm and non-negligent harm insurance policies which apply to this study.

9.5 FUNDING

National Institute for Health Research (NIHR) are funding this study through the Health Services and Delivery Research Programme. Where hospice staff undertake research activity, service support costs will be provided. Funding for sites is laid out in the statement of activities HRA document.

9.6 AUDITS AND INSPECTIONS

The study may be subject to inspection and audit by the University of Kent under their remit as sponsor.

10. STUDY MANAGEMENT

The day-to-day management of phase 2 of the study will be co-ordinated through the Universities of Kent and Cambridge.

11. PUBLICATION POLICY

The results of this proposed research will be of national importance in the UK and of interest to Hospice at Home (H@H) service providers, commissioners and patient groups; these will be the primary targets for dissemination. The outputs from this project will aid and support H@H services to achieve the best outcomes for patients and families at the end of life including assisting them to die at home if this is their preference, without losing sight of a 'good death' experience. Our expected outputs will be guidelines for services and commissioners to help in decision-making and service development of H@H services. The guidelines will show what models/features of H@H services work best and at what cost.

Publication of the full and complete account of the research will be in the NIHR HS&DR Journal. This will allow the research to be freely and publically available via the NIHR journals library website. Results will also be targeted at peer reviewed journals such as such as British Medical Journal, Social Science and Medicine and British Journal of General Practice to reach broad audience coverage in community services, and Health Services Journal to reach service commissioners.

To reflect the likely wide interest in the study findings from patients to policymakers, and capitalise on the potential to improve care, a range of dissemination strategies will be employed to:

- Inform National Policymakers and commissioners
- Reach commissioners through co-applicant links
- Disseminate findings through the existing network of the National Association for Hospice at Home (NAHH) which currently has a membership of 79 organisations and a regular newsletter and annual conference.

• Patients and the Public - A Plain English summary for public and patient engagement and dissemination will be written. This will also be disseminated to our research participants.

The research findings will also be disseminated through presentations at existing research forums such as the European Association of Palliative Care Congress; Clinical Research Network forums; Cicely Saunders Institute, King's College, London; Hospice UK annual conference; National Association for Hospice at Home (NAHH) conference. Findings of the study will be published through press releases of the organisations of the research team and further dissemination through their own newsletters, websites and through social media e.g. Twitter. Finally, dissemination of findings aimed at the public will be facilitated through links with specific organisations including the National Council for Palliative Care.

13. APPENDICES

Appendix 1: Distress Protocol

Post-bereavement, carers will only be contacted after they have received the offer of local bereavement services in order to reduce any potential distress. Any distress encountered is likely to reflect the challenges of caring for someone and grieving for a family member or friend. All data collection will be carried out in person or over the telephone. Therefore, if a participant becomes distressed, the researcher will be able to support and refer participants to further support services straight away. It is possible that carers may become distressed or raise issues during the study that cause concern and/or need for further medical or emotional support. Should this occur, a member of the research team will gain consent from the patient to discuss matters with a relevant support service or the individual's General Practitioner (GP), as appropriate. All of the research team will complete study specific training on addressing distress during data collection for the study.

The following procedures will be followed in order to minimise distress and resolve any situations where distress becomes apparent to the researcher.

Before any interview/questionnaire begins the researcher will inform the participant that:

- They do not have to answer any questions they would rather not answer
- They can pause or stop the interview at anytime
- They can terminate the interview without giving a reason
- The researcher will inform the participant that some of the questions may be distressing or cause them to feel emotions that are common to feel during the grieving process.

During the interview/questionnaire, the researcher should be observant for the following signs of distress:

- Crying - Shaking - Anger - Shouting - Non-responsive to Questions

If the researcher recognises the participant is excessively distressed, they should:

- Stop the interview and acknowledge the participant's distress immediately
- Re-iterate to the participant that they may stop for a break or stop the interview if they are finding it too distressing. They can also withdraw from the study.

The researcher should discuss how the participant would like to proceed using the following options.

STOP interview and withdraw

Take a break/offer another time and day to continue

Continue with the interview

At the end of the interview, acknowledge that the participant was distressed and offer one of the following support options

- Family member or friend who can come before researcher leaves. If no one available straight away ask participant to contact family or friend.
- If no family or friend available. Researcher will offer any required support and ensure participant is comfortable before leaving GP or other support service

Where a participant becomes distressed, the distress log will be completed by the researcher and reviewed by the project team on a monthly basis. Where an occasion of distress requires senior support, the study manager will ensure this is be reviewed by the Chief Investigator as soon as possible and appropriate action taken.
